1.3 Research to be carried out.

In this review, cachexia is a common complication of various advanced malignant tumors, which seriously affects the quality of life and survival time of patients. In view of the clinical problem of non-nutritional response in patients with cachexia, we plan to carry out a clinical case-control study on the intervention of creatine combined with curcumin in patients with cachexia. Overall, we limited the study subjects to upper digestive tract tumors and diagnosed patients with early cachexia. The main purpose of this study is to determine whether the combination of the two can play a positive and stable role in inhibiting the inflammation of cachexia and improving metabolic status, so that basic nutrition can play a role, to reduce the level of skeletal muscle consumption, maintain weight, improve quality of

life, save medical costs, and extend survival time.

2. Purpose of the study

(1) To investigate whether creatine combined with curcumin can improve the inflammatory state, correct the disorder of nutrient metabolism and improve the nutritional status in the early cachexia stage of upper gastrointestinal neoplasms.

(2) To investigate whether creatine combined with curcumin can improve the quality of life and prognosis of patients with early cachexia in upper digestive tract tumors.

3. Study design type, principle, and test procedure

(1) Study Design

Type of study design: prospective open controlled clinical trial; Non-random grouping method: According to the exclusion criteria, patients were included into group A or group B according to their wishes after informed consent; Blind level: This experiment is an open study without blind or emergency letters. Research Center: None.

Group A: basic nutrition treatment, energy 30-35 kcal/kg, protein 1.0-2.0 g/kg, diet deficiency, total nutrition and/or whey protein oral nutrition supplement or tube feeding enteral nutrition supplement.

Group B: Since basic nutrition in group A, creatine 5g/d and curcumin 4g/d were orally added, and the intervention time was 1 month.

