It was assumed that after 4 weeks of oral administration of creatine + curcumin in group B, combined with the existing literature on the improvement of the quality of the bad fluid, the skeletal muscle index at L3 section of CT scan in group B was 20% higher than that in control group A, and the standard deviation was 14%. Bilateral test was required, α was 0.05, the sample ratio between the two groups was 1:1 (i.e., the number of cases in the two groups was equal), $\beta=0.2$. The degree of assurance (test efficacy) $1-\beta=80\%$ was calculated using SPSS software, then the sample size of each group was 68 cases, considering the 10% loss of follow-up rate, each group needed 76 cases, 152 patients in total.

Follow-up test item time point

Classification	Item	0	0.5m	1m	3m
Serological indicators	blood routine	√	-	√	√
	biochemical set	√	-	√	√
	prealbumin	√	-	√	√

	transferrin	√	-	√	√
Body composition index	CT scans skeletal muscle index at L3 cross section	√	-	√	√
	BIA measures muscle mass	√	-	√	√
Inflammatory metabolic indicators	Serum insulin	√	-	√	√
	IL-6	√	-	√	√
	TNF- α	√	-	√	√
	lactic acid	√	-	√	√
	PETCT (SUV)	p.r	-	p.r	-
Physical measurements	Weight	√	√	√	√
	grip strength	√	√	√	√
	skin fold thickness	√	√	√	√
	upper arm circumference	√	√	√	√
nutrition assessment	intake	√	√	√	√
	PG-SGA score	√	√	√	√
Questionnaire Survey	Functional Assessment of Anorexia/Cachexia Therapy(FAACT)	√	√	√	√
	ADL evaluation scale	√	√	√	√

4. Criteria

Inclusion Criteria:

(1) Clinical diagnosis of advanced tumors of the upper digestive tract with untreatable or postoperative recurrence of esophageal and gastric cancer III-IV

- (2) Meet the diagnostic criteria of early cachexia (anorexia and metabolic changes, involuntary body mass reduction $\leq 5\%$ within 6 months)
- (3) Radiotherapy, chemotherapy, or immunotherapy in our hospital
- (4) Understand and fill in a variety of rating scales
- (5) Informed consent, voluntary participation in this study

Exclusion Criteria:

- (1) Neoadjuvant chemotherapy patients
- (2) Intestinal obstruction or gastrointestinal bleeding
- (3) Severe heart, lung and renal insufficiency
- (4) Coagulopathy
- (5) Clinical diagnosis with diabetes and other metabolic diseases
- (6) The expected survival time is less than 1 month
- (7) With cognitive dysfunction or poor coordination
- (8) Allergy to creatine or curcumin
- (9) With a history of drug abuse
- (10) Doctors or researchers deem unsuitable for study participation

Removal Criteria:

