- (1) Do not meet the inclusion criteria and mistakenly included or meet any of the exclusion criteria.
- (2) Meet the inclusion criteria but did not use after inclusion or did not have any record of return visit.
- (3) The intervention measures used during the trial did not conform to the protocol.

Criteria for study termination:

- (1) With allergic reactions or serious adverse events should be stopped according to the investigator's judgment.
- (2) Other complications and special physiological changes occurred during the test.
- (3) During the experiment, the subjects needed parenteral nutrition support during the nutritional support process, and the experiment should be stopped.
- (4) Poor compliance.
- (5) Pregnancy.

5. Research methods and technical route

(1) Research food names and specifications

The creatine provided to the patient in this experimental study scheme was purchased from the sports nutrition food Decathlon creatine powder (powder: 10g/ packet *10 packets/box) produced by Jiangsu Alante Nutrition Co., LTD. Purchased from Meriva Curcumin Phytosome (capsule: 1g/ capsule *120 capsules/box) from THORNE Company, USA.

(2) Treatment plan

Clinical data of patients with advanced esophageal and gastric cancer combined with early cachexia were collected, abdominal CT scan was performed, and the skeletal muscle area and

density of L3 section were measured by Matlab software. Skeletal muscle index was obtained after height correction, and body composition and bone mineral density were measured at the same time. Routine examination and nutritional indexes were determined, including blood routine, biochemical set, prealbumin, transferrin; Inflammatory metabolic markers including serum insulin, IL-6, TNF- α , lactic acid, and PETCT were assessed for metabolism. NRS2002 and PG-SGA scores were performed. According to the standard body weight, dietitians formulated diets for all enrolled patients. According to the ESPEN guidelines and the national industry health standard "Dietary Guidelines for Patients with Malignant Tumors 2017", the dietary energy intake standard was 30-35kcal /kg·d, and the protein intake was 1.0-2.0g /kg·d. The deficiency was given to oral enteral nutrition supplements or whey protein supplements, or to patients requiring tube feeding. Patients were enrolled in group A control group or group B intervention group on a voluntary basis.

Group A intervention group: The above basic nutritional support was provided.

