Group B control group: In addition to the above basic nutrition, oral creatine powder 5g qd, curcumin capsule 2g bid for one month.

The intake, complications and survival of the patients were followed up by telephone for 1 and 3 weeks, physical indicators, nutritional assessment, FAACT and QoL scale were followed up for 2 weeks in the hospital and outpatient department, and nutritional serum indicators, body composition indicators, inflammatory metabolism indicators, physical indicators, nutritional assessment were reviewed for 4 weeks. Evaluation of effect. The long-term survival, re-hospitalization and hospitalization expenses were investigated 3 months later. To evaluate the effect of creatine combined with curcumin on improving the nutritional status, metabolic level and clinical prognosis of alimentary tract neoplasm. Note: Weight is calculated by standard weight: Standard weight (kg) = height (cm)-105.

(3) Combination of drugs

During the study period, patients may have been treated with chemotherapy drugs and immunotherapy drugs due to tumor treatment and may have taken megestrol orally against the oxalic fluid to improve appetite. To avoid the influence of the two groups of therapeutic drugs, the diseases, and drugs of the two groups will eventually be grouped and stratified to eliminate the interference of combined drug use.

(4) Safety evaluation index

- ① Incidence and severity of side effects
- ② The rate of unplanned rehospitalization.

6. Observation of adverse events

Adverse Event (Adverse Event): An adverse medical event occurs after a patient or clinical trial subject receives a drug or a formula for a special medical use, but there is not necessarily a causal relationship.

Serious Adverse Event: An event occurs during the clinical trial that requires hospitalization, prolongates the hospital stay, causes disability, affects the ability to work, threatens life or death, or

results in congenital malformations.

Adverse reaction: an adverse reaction that is harmful rather than expected but is causally related to the application of a drug or special medical use formula food during normal application of the drug or special medical use formula food at prescribed doses. In clinical trials for a new use, all reactions that are harmful and not causally related to the use of a drug or a formula for special medical use, as expected, should be considered adverse when the dose has not been determined.

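### No entry criterion concerns oral intake, but Group B's products are oral only, so patients with no usable oral route can complete Group A and not Group B

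*Combined protocol and SAP*

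**What the plan says.** **Population.** Section 4 admits "untreatable or postoperative recurrence of esophageal and gastric cancer III-IV". The nearest exclusion is "Intestinal obstruction or gastrointestinal bleeding". No criterion mentions dysphagia, oesophageal stenosis, tube dependence or ability to take products by mouth. Exclusion (10) leaves unsuitability to the judgement of doctors or researchers.

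**Basic nutrition.** Section 3(1) includes in Group A's regimen "total nutrition and/or whey protein oral nutrition supplement or tube feeding enteral nutrition supplement". Section 5(2), describing the diet of all enrolled patients before the groups are separated, says "The deficiency was given to oral enteral nutrition supplements or whey protein supplements, or to patients requiring tube feeding".

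**Group B.** Section 3(1): "Since basic nutrition in group A, creatine 5g/d and curcumin 4g/d were orally added, and the intervention time was 1 month". Section 5(2): "oral creatine powder 5g qd, curcumin capsule 2g bid for one month". Section 5(1) gives the curcumin product: "Purchased from Meriva Curcumin Phytosome (capsule: 1g/ capsule *120 capsules/box". (Section 5(2) attaches the labels intervention and control to the wrong groups. I read B as the supplement group, as everywhere else.)

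**Allocation and removal.** Patients choose their group (section 3(1)). The removal criteria in section 4 cover patients who did not use the intervention after inclusion and those for whom "The intervention measures used during the trial did not conform to the protocol". Poor compliance is a termination criterion in section 4. Section 7(3) defines it as medication days below 80% or above 120% of those planned.

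**Analysis.** Section 9 compares the groups with Student's t-test. Section 5(3) mentions stratification by diseases and drugs only.

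**The concern.** A controlled comparison needs both groups to be drawn from patients who could have been in either. Here the text allows one kind of patient into A who cannot complete B: a patient with no usable oral route. This goes beyond the confounding that comes with patient choice. Where both kinds of patient exist in both groups, measured differences can at least be adjusted for. Where one kind has no counterpart in B, a covariate model can only extrapolate.

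Swallowing ability is unlikely to be neutral for the outcomes. Section 1.2.1 names tumour obstruction of the digestive tract as a cause of insufficient intake, and the outcomes include the L3 muscle index, prealbumin, weight, intake and survival. The rules also act after entry. If swallowing worsens during the month, a B patient can be lost through non-conforming intervention or low compliance. Medication-day compliance has no counterpart in A, which takes no study product.

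**Working it through.** **Step 1: follow one patient through the text.** Take a patient with no usable oral route who meets the inclusion criteria.

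| Stage | Chooses A | Chooses B |
|---|---|---|
| Entry criteria | No criterion on oral intake | The same |
| Basic nutrition | Can be given by tube | Can be given by tube |
| Study product | None | Oral powder and capsules: 2 g twice daily at 1 g per capsule = 4 capsules a day |
| Removal for non-use or deviation | Not triggered by the route | Triggered |
| Compliance under 80% of days | No study product to count | Poor, so a termination criterion is met |
| Analysis | Counted in A | Likely not counted |

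The asymmetry follows from the text. It concerns this patient only. A tube-fed patient who can still take powder and capsules by mouth can complete either group.

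**Step 2: the plan's own figures.** The plan states 68 per group, 10% loss, 76 per group and 152 in total. The loss step reproduces: 68 / 0.90 = 75.6, rounded up to 76, and 2 × 76 = 152. The 68 itself does not follow from the stated difference of 20 and SD of 14: 2 × (1.960 + 0.842)² × (14/20)² = 7.7, so 8 per group (9 with the t distribution). That is a separate matter. I use 68 only as the planned number analysed, and 14 as the only SD the plan gives.

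**Step 3: illustration of size.** The documents give neither the share of such patients nor their outcomes, so both are assumptions:

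- s = share of analysed Group A patients with no usable oral route: 5%, 10%, 20%. Group B has none.
- d = how much lower their L3 index is at the analysis: 7 to 14 points, that is 0.5 to 1 SD.
- No true effect of the supplements; 68 analysed per group; SD 14; two-sided 0.05.

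Formulas: false gap = s × d; standard error = 14 × √(2/68) = 2.40; noncentrality = gap / 2.40; rejection probability from the noncentral t with 134 degrees of freedom.

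| s | False gap (points) | Noncentrality | Chance of p<0.05 (nominal 5%) |
|---|---|---|---|
| 5% | 0.35 to 0.70 | 0.15 to 0.29 | 5.2% to 6.0% |
| 10% | 0.70 to 1.40 | 0.29 to 0.58 | 6.0% to 8.9% |
| 20% | 1.40 to 2.80 | 0.58 to 1.17 | 8.9% to 21.2% |

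Simulating the mixture directly, which also widens the spread in A, gives nearly the same: 5.2–5.9%, 5.9–8.7% and 8.7–19.9%.

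**Step 4: direction.** The gap has the sign of d. If d = 0 there is no bias. If tube feeding protects muscle, d is negative and the bias favours A.

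**The case against.** **Tube feeding is part of both groups.** Group B is the basic nutrition plus supplements, so the plan formally provides for tube-fed patients in B. Tube feeding is described as making up a dietary shortfall, which is compatible with partial oral intake, and creatine is a powder. A reader might infer that every tube-fed patient can count only in A. The documents do not support that: they never equate tube feeding with having no oral route, and they neither allow nor forbid another way of giving the products. The objection narrows the affected group but does not empty it.

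**Investigators may decline such patients.** Exclusion (10) permits it, so their admission is inferred from silence. But that criterion gives no guidance, the study is open, and only B needs oral intake. It could be applied to patients who want B and not to those who want A.

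**The affected patients need not be sicker.** Entry weight loss is capped at 5% in 6 months, and a need for parenteral nutrition ends participation. No passage compares outcomes of tube-fed and orally fed patients. A reader might infer that Group A must look worse even if the supplements do nothing. That is plausible but not shown.

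**The size could be overstated.** If 20% of all eligible patients had no oral route and all ended up in A, they would make up 40% of A at 1:1. A deficit of 14 points would then give a 5.6-point gap and a 64% chance of p<0.05. But a patient who chooses B is removed under the plan's rules, not moved to A. If half choose B, the share of A is 20%, as in the last row of the table. In addition, the L3 index is measured at baseline, and in an analysis of change a pre-existing deficit would largely cancel. The plan does not say whether level or change is compared.

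**Choice-based allocation is the larger problem.** This is correct, and curing this point leaves that one in place.

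**Conclusion.** The concern holds for patients with no usable oral route. The entry criteria do not exclude them, Group B's products are specified only as oral, the removal and compliance rules can drop them from B but not from A, and neither the t-test nor the stratification by disease and drugs corrects the imbalance. A bias in favour of B is the likelier direction, but the documents settle neither direction nor size. With the assumed shares of 5% to 20% of Group A and deficits of 0.5 to 1 SD, the false-positive rate runs from close to its nominal value (5.2%) to about 21%. It is lower if change from baseline is analysed, and the bias reverses if tube feeding protects the outcome. The point merits action because leaving the text unchanged lets the two groups draw on different populations, and the remedy is cheap.

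**What to change.** 1. **Common eligibility.** Add one criterion to section 4 and the Summary, applied to both groups before the patient is asked for a preference: able at screening to take the study products by mouth. Alternatively, keep the present entry criteria, restrict the A-versus-B comparison to patients who met this condition at baseline, and report the others separately.
2. **Baseline record.** Record feeding route at baseline, so that the restriction can be applied and any remaining difference seen.
3. **Analysis after entry.** State that patients who lose oral intake after enrolment stay in the analysis of their chosen group, so that the removal and poor-compliance rules do not exclude them from B only. This concerns whose data are analysed, not whether treatment continues.
4. **Reconcile the text.** The sponsor must reconcile the tube-feeding passages in the Summary and sections 3(1), 5(2) and 7 with the oral administration in sections 3(1) and 5(2).

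**Cost.** A sentence in the criteria, a tick-box at screening, one baseline field and a short statement in section 9. Slightly fewer patients will be eligible, and conclusions will be limited to patients with oral intake, which is already true of Group B. None of this cures the wider confounding from choice-based allocation.

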Study Protocol and Statistical Analysis Plan

A prospective open controlled study of creatine combined with curcumin in the intervention of early cachexia in upper gastrointestinal tumors.

NCT number: 05856500

Date: May 12, 2023

Nanjing Drum Tower hospital

The Affiliated Hospital of Nanjing University Medical School

Summary

Project Name	A prospective open controlled study of creatine combined with curcumin in the intervention of early cachexia in upper gastrointestinal tumors
Purpose of the study	
(1) To investigate whether creatine combined with curcumin can improve the inflammatory state, correct the disorder of nutrient metabolism and improve the nutritional status in the early cachexia stage of upper gastrointestinal neoplasms.
 
(2) To investigate whether creatine combined with curcumin can improve the quality of life and prognosis of patients with early cachexia in upper digestive tract tumors.

Study Design	The effect of creatine combined with curcumin on inflammatory state, nutritional metabolism, nutritional state and prognosis of patients with early cachexia of upper digestive tract tumors was investigated in a prospective open controlled study
Total number of cases	152 cases
Criteria	
Inclusion Criteria:
 
(1) Clinical diagnosis of advanced tumors of the upper digestive tract with untreatable or postoperative recurrence of esophageal and gastric cancer III-IV
 
(2) Meet the diagnostic criteria of early cachexia (anorexia and metabolic changes, involuntary body mass reduction $\leq 5\%$ within 6 months)
 
(3) Radiotherapy, chemotherapy, or immunotherapy in our hospital
 
(4) Understand and fill in a variety of rating scales
 
(5) Informed consent, voluntary participation in this study
 
Exclusion Criteria:
 
(1) Neoadjuvant chemotherapy patients
 
(2) Intestinal obstruction or gastrointestinal bleeding
 
(3) Severe heart, lung and renal insufficiency
 
(4) Coagulopathy
 
(5) Clinical diagnosis with diabetes and other metabolic diseases
 
(6) The expected survival time is less than 1 month
 
(7) With cognitive dysfunction or poor coordination
 
(8) Allergy to creatine or curcumin
 
(9) With a history of drug abuse
 
(10) Doctors or researchers deem unsuitable for study participation

Treatment	
1. Patients were enrolled for baseline investigation:
 
(1) Disease status: disease stage, complications, treatment, treatment stage, drug

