The clinical study will develop a data safety monitoring plan according to the risk. All adverse events are recorded in detail, properly handled and tracked until properly resolved or the condition is stable, and serious adverse events and unexpected events are reported to the Ethics Committee, competent authorities, sponsors and drug regulatory authorities in a timely manner in accordance with regulations; The principal investigator conducts regular cumulative reviews of all adverse events and holds investigator meetings where necessary to assess study risks and benefits; For studies with greater than minimum risk, an independent data monitor will be assigned to monitor the study data. For high-risk studies, an independent Data Safety Monitoring committee will be established to monitor the accumulated safety and efficacy data and make recommendations on whether to proceed.

9. Statistical analysis

Statistical analysis was performed using GraphPad Prism version 8.0 (La Jolla, CA, USA). Student's t-test was used for comparison between groups, and one-way analysis of variance (ANOVA) was used for other data. All data are presented as mean \pm SEM. $p < 0.05$ (*) indicates statistical significance. $p < 0.01$ (**) indicates that the difference is more statistically significant.

10. The ethics of clinical research

Clinical research will follow the relevant regulations such as the Declaration of Helsinki of the World Medical Congress. Clinical studies are conducted only after the protocol is approved by the Ethics Committee prior to the start of the study. Before each subject is enrolled in this study, the investigator is responsible to give a complete and comprehensive introduction of the purpose, procedure and possible risks of this study to the subject or his/her agent and sign a written informed consent. Subjects should be informed that they have the right to withdraw from this study at any time, and informed consent should be kept as a clinical study document for future reference. Subjects' privacy and data confidentiality will be protected during the study.

11. Research schedule

Jun 1,2023 to Aug 31,2023: The formal implementation of the project was started. 76 cases were collected, and baseline investigation was conducted for enrolled patients. The patients were not randomly enrolled, and grouped intervention was performed.

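### Radiotherapy can qualify a patient for this self-selected comparison, but the drug-stratification rule does not name it and the section 9 analysis is unadjusted

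*Combined protocol and SAP*

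**What the plan says.** **Eligibility.** Inclusion criterion (3), in section 4 and in the Summary, reads "Radiotherapy, chemotherapy, or immunotherapy in our hospital". Any one of the three is enough. As a treatment, radiotherapy is mentioned nowhere else in the document.

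**Allocation.** Section 3(1) describes non-random grouping: "patients were included into group A or group B according to their wishes after informed consent".

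**Control of background treatment.** Section 5(3), headed as a section on drug combinations, notes that "patients may have been treated with chemotherapy drugs and immunotherapy drugs due to tumor treatment" and that megestrol may be taken. It then says that "the diseases, and drugs of the two groups will eventually be grouped and stratified to eliminate the interference of combined drug use". It gives no list of factors, levels or strata.

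**Analysis.** Section 9 says "Student's t-test was used for comparison between groups, and one-way analysis of variance (ANOVA) was used for other data". The Summary repeats this. Neither mentions a stratum, covariate or propensity method.

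**Data.** The first baseline item in the Summary's treatment plan begins "Disease status: disease stage, complications, treatment, treatment stage, drug", so treatment received is recorded at entry.

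**The concern.** Section 5(3) shows that the sponsor accepts that concurrent anti-tumour treatment can distort the comparison of A with B. Of the three treatments that admit a patient, it names two. The third has no stated control at the design stage, because patients choose their group, and none at the analysis stage, because the test is unadjusted.

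Radiotherapy to the oesophagus or stomach could plausibly affect intake, inflammatory markers and muscle within the 4-week evaluation, and all of these are main or secondary indicators. If its use differs between the groups, part of the observed difference would belong to radiotherapy and be read as an effect of creatine and curcumin. A decision to adjust for it made after the outcomes are seen would be post hoc.

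**Working it through.** **1. Tracing each qualifying treatment through the plan**

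| Treatment | Admits a patient (section 4) | Named in section 5(3) | Carried into section 9 |
|---|---|---|---|
| Chemotherapy | yes | yes | no |
| Immunotherapy | yes | yes | no |
| Radiotherapy | yes | no | no |

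Radiotherapy differs from the other two in the third column. The last column shows that the section 5(3) stratification does not reach the stated analysis for any factor.

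**2. What remains in the estimate**

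- Section 9 followed as written (unadjusted): bias = (radiotherapy share in B − share in A) × (radiotherapy effect on the indicator).
- Section 5(3) strata carried into the analysis: the same product applies within each stratum and is averaged over strata. Imbalance explained by disease or drug regimen drops out; imbalance among patients with the same disease and drugs remains.

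**3. Illustrative size**

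The plan has no figure on this point to reproduce. The inputs from section 3 are 68 evaluable patients per group, 1:1 allocation and two-sided alpha 0.05. The radiotherapy shares and effects are assumptions, because the documents give neither.

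- Standard error of the difference, in SD units: √(2/68) = 0.1715.
- Bias: b = imbalance × effect.
- False-positive rate with no true supplement effect: 1 − Φ(1.96 − b/0.1715) + Φ(−1.96 − b/0.1715).

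Worked case, 20 points and 0.5 SD: b = 0.20 × 0.5 = 0.10 and b/0.1715 = 0.583. The rate is 1 − Φ(1.377) + Φ(−2.543), about 0.084 + 0.006 = 0.090. The non-central t gives 8.9%.

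| Imbalance | Assumed effect (SD) | Bias (SD) | False-positive rate |
|---|---|---|---|
| 10 points | 0.25 | 0.025 | 5.2% |
| 10 points | 0.3 | 0.03 | 5.3% |
| 10 points | 0.5 | 0.05 | 6.0% |
| 20 points | 0.25 | 0.05 | 6.0% |
| 20 points | 0.5 | 0.10 | 9.0% |
| 20 points | 1.0 | 0.20 | 21.5% |
| 30 points | 0.5 | 0.15 | 14.1% |
| 30 points | 1.0 | 0.30 | 41.7% |

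On the plan's SD of 14% for the L3 muscle index, 0.10 SD is 0.10 × 14 = 1.4 percentage points.

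These rates are for a crude imbalance in an unadjusted test. They are not the bias left after stratifying. For example, if disease and drug strata absorbed half of a 20-point imbalance, 10 points at 0.5 SD would remain: 0.05 SD and 6.0%.

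**The case against.** The strongest reply is that section 5(3) is a drug rule and should be judged as one. Its heading and stated aim concern combined drug use. A reader might infer that the plan claims to have removed all interference from background treatment; it makes no such claim. This stands. What remains is that no other section controls background treatment, so radiotherapy has no stated control at all.

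Second, the disease factor is undefined, and the Summary lists treatment under disease status. The rule could be read to include treatment received, and stratifying on site or stage could absorb part of an imbalance. So one cannot say that radiotherapy is clearly excluded, nor that a chemoradiotherapy patient must share a stratum with a patient on the same chemotherapy alone; the plan defines no strata. The text is unclear on the point, and that is itself a reason to name the factor.

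Third, the size is assumed. This also stands. A reader might take the 9% as a forecast, or suppose that radiotherapy patients lean to one group because swallowing capsules is hard for them. Nothing in the documents supports a direction or a mechanism. Nor is it safe to express the bias as a share of the planned effect. A bias of 0.15 SD is 31% of the 0.484 SD that 68 per group detects with 80% power, but only about 10% of the stated assumption (20/14 = 1.43 SD). Those two figures disagree for reasons that belong to a separate point on the sample size.

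Fourth, an unadjusted comparison of self-selected groups leaves other factors exposed too, such as stage and tumour site. That is true and affects the remedy: editing section 5(3) alone would not be enough.

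**Conclusion.** The point holds as a gap in prespecified confounding control. Radiotherapy can qualify a patient, groups are self-chosen, the one stratification rule does not name it, and section 9 adjusts for nothing. A radiotherapy imbalance would therefore remain in the A-versus-B difference, less any part that disease or drug strata absorb if they are used.

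Bias arises only if radiotherapy use differs between the groups and also affects the indicator. Neither can be established from the documents. Under the assumptions shown, the consequence runs from negligible to material, with about 9% false positives in the 20-point, 0.5 SD case. The documents do not support saying that the supplement effect is biased, only that the plan would not remove such a bias. Because the remedy is cheap and must be set before outcomes are analysed, it should be made.

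**What to change.** - **Section 5(3):** replace the undefined factors with a prespecified list: radiotherapy (yes/no, in use or planned at enrolment), chemotherapy, immunotherapy, megestrol, and disease, stating what disease means (for example tumour site and stage).
- **Section 9:** for the main indicators, replace the unadjusted t-test with a model containing group and these factors, for example ANCOVA on the baseline value of the indicator. Without this change the section 5(3) list has no effect on the result.
- **Reporting:** give the radiotherapy share by group in the baseline table.

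**Cost.** Treatment is already a baseline item, so no new data are needed. If the four treatments, site and stage are each two-level, six factors plus the baseline value use 7 degrees of freedom. With 2 × 68 = 136 evaluable patients, the residual falls from 134 to 127. Model terms avoid the sparse cells that full cross-stratification would create. The software must be able to fit the model. Adjustment deals only with the factors listed; it does not make a self-selected comparison equivalent to a randomised one.
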